The results of our recent LMA trial indicate that surfactant delivery via LMA produces immediate improvements in oxygenation comparable to delivery via ETT, and decreased need for subsequent ventilatory support. However, because our previous INSURE approach for ETT delivery of surfactant included morphine, a slow-onset, long acting analgesic which likely contributed to the need for invasive ventilation, it remains unclear whether LMA delivery of surfactant is as effective as our new INSURE technique, which is designed to avoid respiratory depression.

Since our last trial began, the results of a small randomized trial were published, where the 11 babies who received surfactant via LMA showed improvements in oxygenation comparable to those in our study, whereas no change occurred in the surfactant-untreated (CPAP-only) group (Attridge, Stewart, Stukenborg, & Kattwinkel, 2013). In a piglet model of RDS, surfactant administered via LMA had physiologic effects similar to those of ETT administration (Roberts et al., 2010). The only ongoing clinical trial on delivery of surfactant via LMA to human neonates with RDS (Roberts et al., NCT01116921 at www.clinicaltrials.gov) is examining the effectiveness of this procedure (versus no surfactant treatment) in decreasing the need for later mechanical ventilation.

From the foregoing, it is apparent that clinical trials are still needed to address the relative efficacy of surfactant delivered via LMA versus optimized INSURE approaches. In this proposal, we extend our investigations of surfactant delivery by LMA to the current clinical context in which premedication for INSURE comprises atropine and remifentanil.

Hypothesis:

Surfactant therapy delivered via LMA is not inferior to surfactant therapy delivered via transient intubation (INSURE technique) with short-acting narcotic premedication for mild to moderate RDS in preterm neonates.

Aims:

1. To compare the rate of failure of surfactant therapy delivered via LMA to the rate of failure of surfactant therapy delivered via transient intubation (INSURE technique) in avoiding mechanical ventilation in neonates 27 to 36 weeks' gestation with mild to moderate RDS.

1a. To evaluate the success of remifentanil as premedication for transient intubation (INSURE technique) as compared to morphine used in our previous trial.

2. To further evaluate the safety of surfactant administration via LMA.

B. Study Design/C. Subject Population

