- The neonates randomized to standard management will be given premedication with atropine (0.1 mg/kg) and remifentanil (2 mcg/kg) for endotracheal intubation according to the new standard AMC premedication order sheet.
- A CO₂ detector will be used to verify endotracheal intubation
- Surfactant (Infasurf) therapy will be delivered via ETT, at a dose of 3mL/kg, in 2 aliquots. Surfactant is drawn up in a syringe with a Luer adaptor.
- This is followed by positive pressure ventilation (PPV) for a minimum of 5 minutes before extubation to nasal CPAP (if possible) by 15 minutes after completion of surfactant therapy.
- However, the baby will remain intubated and continue to mechanical ventilation via ETT if one or more of the following occurs:
 - Persistent apnea
 - If this is thought to be related to sedative medication, a one-time dose of naloxone (0.1 mg/kg) may be administered as part of the study protocol
 - Severe retractions (as judged by an attending neonatologist or fellow)
 - Inability to wean FiO₂ < 0.60 to maintain target SpO₂ 90-95%
- Management of RDS, mechanical ventilation, concurrent neonatal issues, and any complications that may arise will be at the discretion of the clinical care team.

• **LMA group: Atropine + LMA + Infasurf**

- The neonates randomized to LMA management will be given atropine (0.1 mg/kg) before the insertion of the size 1 classic LMA. The LMA cuff will be inflated with 2-4 mL of air.
- A CO₂ detector will be used to verify the placement of the device.
- Adequate PPV will be verified by observing adequate chest movements and SpO₂ for at least 1 minute.
- The tip of a T-connector (or, a 5-French catheter) will be cut to reach the distal end of the LMA, to instill a 3 mL/kg dose of Infasurf in 2 aliquots.
- Surfactant will be drawn up in a syringe with a Luer-type adaptor.
- Following surfactant therapy, manual PPV will be provided for a minimum of 5 minutes.

- After spontaneous respirations are judged adequate, the LMA will be removed and nasal CPAP resumed.
- Indications for intubation to initiate assisted ventilation will be one or more of the following:
 - Persistent apnea
 - Severe retractions (as judged by an attending neonatologist or fellow)
 - Inability to wean $\text{FiO}_2 < 0.60$ to maintain target $\text{SpO}_2 90\text{-}95\%$
- Management of RDS, mechanical ventilation, concurrent neonatal issues, and any complications that may arise will be at the discretion of the clinical care team.

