The sample size was estimated based on results from the recent study on this population, at the Albany Medical Center NICU. We will thus expect that 30% of the LMA group will meet failure criteria, i.e., the LMA success rate in avoiding later intubation and ventilation will be 70%. For a non-inferiority design, with a clinically relevant non-inferiority margin of 20%, a sample of 130 patients (65 per group) will be needed to conclude non-inferiority of the LMA method compared to INSURE (calculated using a one-sided $\alpha=0.05$, β error=0.20).

➤ Secondary outcome measures:

Groups will be analyzed for secondary outcome differences using chi-square statistics for categorical data, and t-test or non-parametric tests for continuous data, as appropriate for the distribution obtained. The FiO_2 response to surfactant treatment strategies will be compared from baseline to 1 and 8 hours using repeated measures ANOVA and post-hoc Dunnett's test. Time to wean off respiratory support will be compared between groups using Kaplan-Meier analysis, with censoring at discharge.

➤ Interim Analyses:

Reports for the IRB will be prepared after one year of initiation of the trial or enrollment of 50 patients, whichever comes first. Data on the primary outcome, mortality, and major adverse events on the first 50 patients, will be submitted to [name] for purposes of safety monitoring. A difference in primary outcome at the $p<0.01$ level, or a consistent trend towards differences in major adverse events will constitute criteria for recommending that the study be stopped.

E. Risks

- Risk category: Greater than minimal.

This study is considered as a greater than minimal risk study. The study design includes a decreased use of laryngoscopy for tracheal intubation, which is currently the standard method of surfactant delivery. Laryngoscopy is associated with apnea, minor abnormalities in cardiac rhythm, obstructed respiration, increase in systolic blood pressure, decreased heart rate and transcutaneous oxygen tension in preterm neonates during the laryngoscopy (Carbajal, 2007)

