Reporting period: AEs will be recorded from the time of informed consent until 72 hours following the last use of the LMA or ETT for non-serious AEs, and until 30 days after the last use of the LMA or ETT for serious AEs. Any AE that occurs between the time informed consent is obtained and the initial airway insertion, that is considered related to a protocol-specified procedure, must be reported.

Procedures for assessing, recording and reporting AEs: Throughout the duration of the study, the investigators will closely monitor each subject for clinical evidence of device-related events, and monitor all clinically information for evidence of AEs. AEs not explained by the infant's underlying illness which occur during the course of the study will be reported in detail on the appropriate forms to the IRB, and followed until resolved or stable. All serious AEs will be reported to the IRB within 24 hours.

Grading of AEs:

- Mild - sign or symptom noticeable, but easily tolerated by the patient, and not expected to have a clinically significant effect on the baby's overall health and well-being. Not likely to require specific medical attention.

- Moderate - causes interference with usual function or affects clinical status. May require medical intervention.

- Serious - incapacitating or significantly affecting clinical status. Likely requires medical intervention and/or close follow-up.

Expected adverse events (AEs):

The following AEs associated with prematurity, the clinical course of RDS, or treatments for these conditions, are expected with the approximate frequencies listed in the Table. These AEs are actually or may be potentially relevant to the LMA study protocol.

Adverse events	Expected %
During surfactant administration procedure	
Desaturation > 1 min	5% to 20%
Airway obstruction	39%
Bradycardia	34%
Surfactant reflux onto CO ₂ detector	5%
Re-intubation	5%
LMA replacement	5 to 10%
Others (observer, specify):	
Clinical complications of prematurity and RDS	
Pneumothorax	6 to 17%
Other pulmonary air leak	15%
Pulmonary hemorrhage	1 to 7%
Hypotension	15%
Oliguria	10%
Intraventricular hemorrhage (grade \geq 2)	0.5% to 10%
Relevant Outcomes	
Chronic lung disease	5% to 15%
Mortality (depends on gestational age)	1% to 5%

Serious adverse events (SAE):

A SAE is defined as an adverse effect that meets any of the following serious outcomes:

- o Is fatal;
- o Is life-threatening;
- o Results in persistent or significant disability;

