- o Is an important medical event for which the subject may require medical or surgical intervention to prevent the outcomes above described;
- o It requires or prolongs inpatient hospitalization

SAEs will be recorded from the time of informed consent until the baby is discharged or removed from the study. A Serious Adverse event form must be completed and signed by the principal investigator, and submitted to the IRB within 24 hours after the event. Furthermore, the investigator will complete and submit follow-up SAE information including diagnosis, outcome, and results of specific investigations.

The intensity or severity of SAEs:

- SAEs will be classified as possibly related (little or no relationship with the study), probably related (likely to be related to the study) or definitely related (a strong relationship with the study).
- If a SAE is believed to be at least possibly related to the study device, it will be additionally reported to the manufacturer and the FDA.

F. Benefits:

There are no economic benefits for subjects or their families for participating in the research. The medical benefits will be evaluated as result of the research.

G. Confidentiality:

Every subject will have an identification code number (ICN) after the randomization that will identify the therapeutic method. The data collection form will have the ICN. All the data will be

stored in password protected files on a computer in the Neonatology fellows' office. There will be two password protected files. The final dataset for analysis will be de-identified, including only the subjects' ICN and the study data. The second dataset will include the subjects' name, MR number, date of birth and the ICN; this file will be used for cross-verification only, if needed.

The principal investigator and/or co-investigator or study coordinator will release the preliminary information only to the IRB. Significant device-related adverse event information will be communicated to the IRB, the LMA manufacturer, and the FDA. Final aggregate data will be posted on clinicaltrials.gov, and submitted for publication.

H. Options

The subjects that could be potentially enrolled in the trial, but whose parents do not agree to participate will receive the standard of care for patients with RDS, as outlined in the ETT group, and including premedication, intubation, rescue surfactant therapy and respiratory support as needed.

Sponsor/materials:

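### Non-serious adverse events are recorded until 72 hours after the last LMA or ETT use, so ventilated infants are observed longer and raw counts are not comparable if ventilation differs between arms

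*Combined protocol and SAP*

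**What the plan says.** Section E (Risks), Reporting period, records adverse events from consent. Recording ends "until 72 hours following the last use of the LMA or ETT for non-serious AEs". The same paragraph sets a later end where the event is serious: "until 30 days after the last use of the LMA or ETT for serious AEs". A later paragraph of section E, under Serious adverse events, gives another end: "SAEs will be recorded from the time of informed consent until the baby is discharged or removed from the study".

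Study/Intervention determines how long a device is in use. In the INSURE arm the plan is "extubation to nasal CPAP (if possible) by 15 minutes after completion of surfactant therapy", but if stated respiratory criteria are met "the baby will remain intubated and continue to mechanical ventilation via ETT". In the LMA arm the mask is removed once breathing is adequate, and a list introduced by "Indications for intubation to initiate assisted ventilation will be one or more of the following" leads failing infants to an ETT.

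Two places make use of adverse events. Aim 2 is "To further evaluate the safety of surfactant administration via LMA". Section D, Interim Analyses, says that "a consistent trend towards differences in major adverse events will constitute criteria for recommending that the study be stopped". Neither place gives a common observation window or an exposure-adjusted analysis.

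**The concern.** The end of the window is set by something that happens after randomisation and is closely tied to the primary outcome, avoidance of mechanical ventilation in the first 120 hours of life. A success has the device in place for minutes and is then observed for about 72 hours. A ventilated infant is observed for 72 hours beyond the end of ventilation.

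If one arm ventilates more infants, or ventilates them for longer, it accumulates more observation time and so more recorded events, even when the risk per day is the same. The distortion can run either way: it favours whichever arm needs less ventilation. At stake is the reading of non-serious event totals as evidence on LMA safety under Aim 2.

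**Working it through.** **Inputs from the protocol.** Windows of 72 hours (3 days) and 30 days after last use (section E); 30% expected LMA failure and a 20-point margin (section D, Sample size).

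**Assumptions.** The protocol gives no expected ventilation time and no separate INSURE failure rate. I take v = 3 or 7 ventilated days (wider range 1 to 14), and 30%, 40% or 50% failure in the other arm; 50% is 30% plus a gap the size of the margin. Every failure is ventilated from day 0, and the daily hazard is constant and equal in both arms.

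**1. The plan's own figure.** The adverse-event window has no calculation behind it; the computable design figure is the sample size. With 70% success in both arms, n per arm = (1.645 + 0.842)² × 2 × 0.70 × 0.30 / 0.20² = 6.185 × 10.5 = 64.9, so 65 per arm and 130 in total. This matches the protocol.

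**2. One infant, non-serious events.** A success is observed for 3 days and a failure for 3 + v days. The ratio (3 + v)/3 is 2.0 at v = 3 and 3.3 at v = 7.

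**3. Arm means, non-serious events.** Mean observation = 3 + f·v days, where f is the failure rate.

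| Failure rates | v = 3 | v = 7 |
|---|---|---|
| 30% vs 30% | 3.9/3.9 = 1.00 | 5.1/5.1 = 1.00 |
| 40% vs 30% | 4.2/3.9 = 1.08 | 5.8/5.1 = 1.14 |
| 50% vs 30% | 4.5/3.9 = 1.15 | 6.5/5.1 = 1.27 |

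At 50% vs 30%, the ratio runs from 3.5/3.3 = 1.06 (v = 1) to 10.0/7.2 = 1.39 (v = 14). At constant hazard, expected event counts are in the same ratio.

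**4. Proportion of infants with an event.** Take a hazard giving 15% in 3 days, and v = 5. A failure observed for 8 days has probability 1 − 0.85^(8/3) = 0.352. At 30% failure the arm shows 0.7 × 0.15 + 0.3 × 0.352 = 21.1%. At 50% it shows 0.5 × 0.15 + 0.5 × 0.352 = 25.1%. That is a gap of 4 points with no difference in daily risk.

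**5. Serious events under the 30-day rule.** Mean observation = 30 + f·v days. At 50% vs 30%, the ratio is 31.5/30.9 = 1.02 (v = 3) and 33.5/32.1 = 1.04 (v = 7). Under the discharge-or-removal rule, the end does not depend on last device use.

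**6. Fixed window.** With the same calendar window for every infant, the ratio is 1.00 whatever the failure rates, apart from death or transfer.

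**The case against.** The best counter-argument is that the main safety comparisons do not use this window. Pneumothorax or pneumomediastinum, BPD, insertion complications and mortality are separate secondary outcomes, and all infants stay in data collection to discharge. Section D describes no between-arm test of total non-serious events. This stands, and it limits the point to how adverse-event totals are read for Aim 2.

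The assumptions can also be challenged. The protocol nowhere expects 50% failure, and its sample size reproduces with equal success rates. Some late-failure criteria (sustained high FiO₂, an early second dose, more than two doses) need not mean prolonged ventilation. Six named items in the expected-event table, including the most frequent (airway obstruction 39%, bradycardia 34%), are listed under the administration procedure, so a constant hazard overstates the effect. These points reduce the size but do not remove the problem. The same table lists hypotension (15%), oliguria (10%) and other air leak (15%) as complications of prematurity and RDS, not of the procedure. Two features work the other way: repeat dosing also resets last use, and an infant intubated on day 2 and ventilated for 3 days is observed for 2 + 3 + 3 = 8 days, against 6 in the formula.

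If last use meant use for surfactant delivery only, most of the effect would disappear. The text does not say so.

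Lastly, events during later ventilation or repeat dosing are real consequences of the assigned strategy and should not be lost. That is correct, and the fix has to keep them visible by arm.

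**Conclusion.** The point holds for non-serious events: their observation time depends on ventilation, so raw counts or proportions cannot be read as risk differences when ventilation rates or durations differ. The illustrative excess is about 15% to 27% in the arm with more failures, given 50% vs 30% failure, 3 to 7 ventilated days from day 0 and a constant equal hazard. It is zero if failure rates and durations are equal. The primary outcome and the sample size are unaffected.

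A reader might infer two stronger conclusions that the documents do not support. The first is that serious events are distorted to the same degree. Under the 30-day rule the figure is about 2% to 4%, and the competing discharge-or-removal rule is not tied to device use. The two passages conflict and must be reconciled. The second is that the artefact could drive the interim stopping criterion. That criterion concerns major adverse events, which the protocol does not define. If major means serious, the effect is small or not governed by last use, and the 15% to 27% does not apply. Nor do the documents show that either arm in particular would be disadvantaged.

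**What to change.** Leave the current window in place for recording and reporting individual events. Add to section D that between-arm comparisons of non-serious events count, in every infant, those from randomisation (or the start of premedication) to 72 hours after first device insertion, and that later events are tabulated separately by arm.

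The count should not start at insertion. Premedication comes before it, and remifentanil is planned only in the INSURE arm, so that start would drop drug reactions from one side of the comparison.

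No new data are needed for the non-serious comparison: recording begins at consent, procedure-related events before insertion must already be reported, and last use is never earlier than first use.

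For serious events, reconcile the two end dates, then apply one common fixed window, including for the interim comparison. Check coverage when choosing it: under the discharge-or-removal rule, an infant discharged before day 30 would not be covered to day 30.

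The cost is a few sentences of text. The downside is that later events linked to repeat dosing or ventilation leave the main comparison and appear only in the separate table.

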Although the study interventions are limited to the airway used for surfactant administration in the first 1 to 3 days of life, and clinical management or follow-up are not otherwise conditioned by the study, all subjects enrolled will continue in the study up to discharge from AMC, for the purposes of data collection. This will include:

- the FiO₂ and mode of respiratory support before enrollment and at 0, 1, 12, 24, and 48 hours, and 7 and 28 days after initial surfactant administration,
- any need for additional doses of surfactant,
- any need for intubation, and
- any need for mechanical ventilation.

D. Data Analysis

A copy of the data collection sheet that will be used for the study is included.

Primary Outcome Measures: The primary outcome will be success of the surfactant administration strategy in avoiding mechanical ventilation in the first 120 hours of life.

Secondary Outcome Measures:

- Number of surfactant doses
- Days on assisted ventilation
- Day on any noninvasive respiratory support (CPAP/NIPPV modes)
- Days until off respiratory support (supplemental oxygen and/or pressure support)
- Rate pneumothorax and/or pneumomediastinum
- Rate of BPD as defined by oxygen dependence at later of 28 days or 36 weeks' postmenstrual age
- Complications during insertion of LMA or ETT
- Mortality rate

Planned post-hoc analyses include timing of failure by treatment group, which should illuminate the mechanisms of failure by treatment strategy.

➤ Baseline comparability:

Baseline differences between ETT group and LMA group will be compared using t-tests for continuous variables (birth weight, gestational age, age and FiO₂ at enrollment) and chi-square test for categorical variables (race, sex, prenatal care, antenatal steroids, mode of delivery, multiple gestation)

➤ Primary outcome measure:

Our primary outcome for the study is the proportion of infants that will reach the early and/or late failure criteria. The incidence of the failure criteria will be compared using chi-square statistics.

➤ Sample size/Power analysis:

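### Two unreconciled end points for recording serious adverse events, and a causality scale on which an unrelated event must be graded possibly related

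*Combined protocol and SAP*

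**What the plan says.** The combined protocol and SAP defines SAE recording twice in section E (Risks). Both statements start at informed consent.

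- *Reporting period* continues "until 30 days after the last use of the LMA or ETT for serious AEs".
- *Serious adverse events (SAE)* states: "SAEs will be recorded from the time of informed consent until the baby is discharged or removed from the study".

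The description of data collection just before section D adds that "all subjects enrolled will continue in the study up to discharge from AMC, for the purposes of data collection". The study design names three participating centers, each with its own IRB.

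On reporting, *Procedures for assessing, recording and reporting AEs* says "All serious AEs will be reported to the IRB within 24 hours", and the SAE text repeats the 24-hour limit.

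On causality, the text under *The intensity or severity of SAEs* offers three grades. The lowest is given as: "SAEs will be classified as possibly related (little or no relationship with the study". The other two are *probably related* and *definitely related*. The next bullet sets the outside-reporting rule: "If a SAE is believed to be at least possibly related to the study device, it will be additionally reported to the manufacturer" and to the FDA. Section G (Confidentiality) adds: "Significant device-related adverse event information will be communicated to the IRB, the LMA manufacturer, and the FDA".

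**The concern.** There are two separate faults.

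The first is a conflict between two operative rules. They cover the same infants and the same events and stop at different times. The documents state no order of precedence and no whichever-is-later rule. Two centers could each follow one statement faithfully and hold different SAE records. The 24-hour report to the IRB does not repair this, because an event after the end point that a center follows may never be recorded and so never sent.

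The second is a scale whose bottom grade contradicts its own label. An SAE with no relationship to the study can only be recorded as *possibly related*.

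What is at stake is the completeness and attribution of the safety record, which is the subject of Aim 2 (safety of surfactant given by LMA). The interim review of major adverse events in section D would be touched only if it draws on these SAE records, which the documents do not say.

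**Working it through.** **SAE window.** The documents give no figure to reproduce, so the two end points are set against each other.

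Inputs from the documents: gestational age at birth 27 0/7 to 36 6/7 weeks in three strata; enrollment before 48 hours of age; one window ending 30 days after last device use; the other ending at discharge.

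Assumptions, not in the documents: treatment at 1 day of age; last LMA or ETT use that same day; discharge at 35, 36 or 37 weeks' postmenstrual age (PMA), but not before day 7 after treatment.

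Formulas, with GA in days:

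- Discharge day after treatment: D = max(7, 7 × PMA weeks − GA − 1)
- Gap: G = D − 30. Positive means the discharge window runs longer; negative means the 30-day window does.

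Example: GA 27 0/7 is 189 days; at 36 weeks, D = 252 − 189 − 1 = 62 and G = +32.

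| GA at birth | GA, days | G at 35 wk | G at 36 wk | G at 37 wk |
|---|---|---|---|---|
| 27 0/7 | 189 | +25 | +32 | +39 |
| 28 6/7 | 202 | +12 | +19 | +26 |
| 29 0/7 | 203 | +11 | +18 | +25 |
| 32 6/7 | 230 | −16 | −9 | −2 |
| 33 0/7 | 231 | −17 | −10 | −3 |
| 36 6/7 | 258 | −23 | −23 | −23 |

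In the last row the day-7 minimum applies: 7 − 30 = −23.

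The windows coincide when 7 × PMA − GA − 1 = 30, so GA = 7 × PMA − 31. That is 214, 221 or 228 days (30 4/7, 31 4/7 or 32 4/7 weeks) for discharge at 35, 36 or 37 weeks. All three fall inside the middle stratum, so under these assumptions the sign of the disagreement changes within the trial's own population.

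Sensitivity:

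- Treatment at 0 or 2 days of age moves G by one day, except where the day-7 minimum applies.
- Each day of ETT use after the treatment day moves the 30-day end point one day later and lowers G by one. With 10 such days, the youngest stratum goes from +12 to +39 down to +2 to +29, and 33 0/7 weeks goes from −17 to −3 down to −27 to −13.
- Other assumptions: last device use on day of life 1 to 3, so the 30-day window closes on day 31 to 33. A 27 0/7-week infant discharged at 36 to 40 weeks' PMA (day of life 63 to 91) gives 63 − 33 = 30 to 91 − 31 = 60 days in favor of the discharge window. A 36 6/7-week infant discharged on day of life 5 to 14 gives 31 − 14 = 17 to 33 − 5 = 28 days in favor of the 30-day window. The reversal is the same.

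**Causality scale.** There are three grades: possibly, probably, definitely. The trigger is at least possibly related. All 3 of 3 meet it, so if this scale is the one applied, no SAE is excluded.

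As an illustration of the label, fatal events are SAEs by definition and the expected-events table gives mortality of 1% to 5%: 0.01 × 130 = 1.3 and 0.05 × 130 = 6.5. About 1 to 7 deaths would therefore be graded at least *possibly related* whatever their cause.

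**The case against.** **The two end points could both be obeyed by recording to the later date.** They could, but that rule is not written anywhere. It is the proposed remedy, not the current text.

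**The day counts rest on assumed discharge ages and same-day last device use.** This stands. Later ventilation by ETT shrinks one gap and enlarges the other. The counts are an illustration only; the conflict itself needs no assumption about length of stay beyond some infants leaving before, and some after, the 30-day point.

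**The outside-reporting trigger is a separate judgment.** This also largely stands. The scale refers to the study and the trigger to the study device, and section G points to the LMA. A reader might infer that the trigger is unworkable, or that it is unclear whether it covers the ETT. The documents support no more than missing detail there. If the scale does feed the trigger, the result is over-reporting, which loses no signal. The upper two grades still mark likely-related events, and reporting to the IRB does not depend on the grade.

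**The AE procedures already ask about the underlying cause.** They do, by singling out AEs for which the baby's own disease does not account: "underlying illness which occur during the course of the study will be reported in detail on the appropriate forms to the IRB". But that sentence governs AE reports to the IRB and adds no grade to the SAE scale. The SAE form is not in the text available, and an unseen form does not correct a scale stated in the protocol.

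**Chronic lung disease.** A reader might infer that cases diagnosed after the 30-day point would be lost. The documents do not support that: BPD is collected as a secondary outcome in any event, and not every case need be an SAE.

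**Conclusion.** Both faults hold on the text. The SAE end points conflict, neither window contains the other over the eligible gestational ages, and an SAE required by one statement can go unrecorded and unreported to the IRB under the other. How many SAEs fall in the disputed days cannot be computed, because the documents give neither lengths of stay nor the timing of SAEs.

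The causality scale forces an unrelated SAE into *possibly related*. The consequence is blurred attribution under Aim 2 and, if the scale feeds the trigger, over-reporting to the manufacturer and FDA.

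It would be wrong to go further. No bias between arms is shown. The primary analysis, the sample size of 130 and the secondary outcomes listed in section D are unaffected. This should be corrected, but it does not threaten the trial's main conclusion.

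**What to change.** 1. Reconcile *Reporting period* and *Serious adverse events (SAE)* to one SAE end point that drops no event either now covers, for example the later of discharge and 30 days after last LMA or ETT use. Say how it applies to infants removed from the study.
2. Align the data-collection paragraph with it, so that discharge means discharge from any of the three participating centers rather than AMC alone.
3. Add a *not related* grade and limit *possibly related* to events with some possible relationship, however small, so that no such event leaves the trigger.
4. Use the same referent for the scale and the trigger.

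The cost is wording in those paragraphs and on the SAE form. Infants discharged before the 30-day point need a contact or chart check up to it. The 30-day rule already implies that work, although no step for it is described. Infants in hospital beyond that point are already to be recorded to discharge under the other statement.
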